4.3.2 Spontaneous Breathing Trial (SBT) and Extubation/Deconnection

When PaO_2/FiO_2 is no lower than 200 mm Hg at $PEEP \leq 8 \text{ cmH}_2\text{O}$, the patient will be considered to have an acceptable gas exchange on 8-5 cmH_2O of PEEP and will be deemed capable to tolerate this setting.

A 30-120 minute spontaneous breathing trial (SBT) will be initiated as the following criteria are met and whether a patient tolerated fully assist ventilation with $PEEP \leq 8 \text{ cmH}_2\text{O}$ for at least 4 hours without experiencing hypoxemia ($SpO_2 < 88\%$ ora $PaO_2/FiO_2 < 150 \text{ mmHg}$):

- improvement or resolution of the underlying cause of acute respiratory failure;
- correction of arterial hypoxemia ($PaO_2 \geq 60 \text{ mmHg}$ at a $FiO_2 \leq 0.4$ with $PEEP \leq 8 \text{ cmH}_2\text{O}$);
- absence of fever ($\geq 38^\circ\text{C}$) or sepsis;
- blood hemoglobin concentration of 7 g/dL or more;
- hemodynamic stability without cardiac ischemia or arrhythmias (norepinephrine $< 0.1 \text{ gamma/kg/min}$).

Success of the spontaneous breathing trial will be defined as presence of the following criteria:

- respiratory rate $< 35/\text{min}$;
- arterial oxygen saturation $\geq 90\%$;
- heart rate $< 120/\text{min}$;

- systolic blood pressure > 90 and < 160 mmHg;
- adequate cough.

If the spontaneous breathing trial is successful, the patient will be extubated or disconnected from the mechanical ventilator if tracheostomized. In case of SBT failure, mechanical ventilation will be resumed (with any PEEP levels accepted, according to the strategies described above

Data about extubation/deconnection will be collected immediately before extubation and 20 minutes following extubation. The need for a tracheostomy will be recorded in the CRF as well as the incidence of adverse events, i.e., the need for reintubation, infection rate, death. After the discharge from ICU, the enrolled patients will be followed until discharge from the hospital.

4.4 Observation period for the primary endpoint

This period covers the interval over which the subject may qualify for the primary endpoint of the study. It starts with the randomization and ends 72 hours after randomization. After this period the treatment duration will be dependent on the subject's clinical course and the investigator's judgment on the perceived need to continue the study drug. The use of TTS-fentanyl will not be allowed in remifentanil alone group even after the end of the observation period for the primary outcome.

4.5 24-hour safety follow-up period

This period starts with the permanent discontinuation of the study drug (TTS-fentanyl) and ends 24 hours later. Subjects must not be discharged from the hospital until the end of this period.

New Adverse Events occurring in this period are recorded in the case report form (CRF).

4.6 End of Study (EOS) visit (individual subject)

This visit occurs at the discharge from the intensive care unit or in case of death after the observation period for the primary endpoint and is defined as the last visit performed by an individual subject for the study. This visit may occur earlier for subjects who prematurely withdraw from the study.

In this visit we will record:

- An Arterial Blood Gases (ABG) sample will be collected and ABG parameters recorded (pH, PaCO₂, PaO₂, HCO₃⁻, Lactates, SaO₂);
- Glasgow Coma Scale, RASS;
- Respiratory parameters: Ventilation mode, Pressure Support, Respiratory Rate, Tidal Volume, peep, FiO₂, EtCO₂; if patient is spontaneously breathing: FiO₂, RR, SpO₂;
- Hemodynamic parameters (Heart Rate, SBP/DBP/MAP);
- Data on the global duration of opioid therapy/length of stay (LOS) in hospital and ICU.

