to intravenous opioids during the weaning phase from mechanical ventilation and the post-extubation period until the discharge from ICU to the ward. There is only a case-report documenting the use with success of TTS-fentanyl for a patient who developed central hyperventilation(Adachi et al. 2007).

Our hypothesis is that, due to the intrinsic pharmacokinetics and pharmacodynamic characteristics of TTS formulation of fentanyl, it can have a role in weaning the patient from intravenous opioids, such as remifentanil, and mechanical ventilation, reducing the duration of MV itself. It can have also an impact on costs allowing the discharge to the ward of patients with an ongoing patch.

2. Study Objectives and Endpoints

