8.2 Reporting of adverse events

All AEs with an onset date and time from study drug initiation up to 24 hours after study treatment discontinuation (i.e., the 24-hour safety follow-up period) must be recorded on specific AE forms of the CRF. Those AEs occurring from the signature of the informed consent form until End of Study will also be recorded on an AE form in the CRF if they are believed to be related to a protocol-mandated procedure.

Information to be collected in an AE form in the CRF includes date and time of onset, action taken with the study treatment, outcome of AE, date of resolution (if applicable) and PI's assessment of seriousness and intensity, and relationship to study treatment, study design or protocol mandated procedures. For AEs related to cardiac rhythm abnormalities, additional ECG parameters may be collected.

If the intensity of an AE worsens during study treatment administration, only the worst intensity should be reported on the AE form. If the AE lessens in intensity, no change in the severity is required to be reported.

For AEs ongoing at the start of study treatment, the worsening of the AE after the start of study treatment will be recorded as a separate AE with the new intensity.

Follow-up information on any ongoing AEs obtained after the subject's EOS visit will not be collected in the CRF.

9. Risk-Benefit Assessment

In an ICU setting, in which patients are continuously monitored 24 hours a day and mechanically ventilated, it can be stated that the risks related to the use of TTS-fentanyl are few. There is obviously a consistent risk of developing an opioid addiction, already present using remifentanil, that compared to fentanyl is stronger and short-acting. Respiratory depression is easily and early detected. On the other hand, an alternative and "needle-free" route of administration of an opioid,

fentanyl, that is different from a pharmacokinetic point of view if compared to remifentanil, could help in IV opioids weaning, it can reduce the length of mechanical ventilation, and length of stay in ICU, decreasing the risks related to the stay in an ICU setting as infections rate and increases in costs. Moreover, TTS-fentanyl could theoretically be exported out from the ICU to the medical wards, allowing more gradual and physiological weaning from opioids.

10. Data handling

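### End of Study is set at ICU discharge, so outcomes of adverse events ongoing then, or starting later on the ward, are not collected, and hospital stay is listed before it can be known

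*Combined protocol and SAP*

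**What the plan says.** On the timing of EOS, section 4.6 states: "This visit occurs at the discharge from the intensive care unit or in case of death after the observation period for the primary endpoint". It adds that this visit "is defined as the last visit performed by an individual subject for the study". Among the items to be recorded then is "Data on the global duration of opioid therapy/length of stay (LOS) in hospital and ICU". Table 1 repeats both the timing and the item.

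Other sections reach beyond that point:

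- **Section 4.3.2:** "After the discharge from ICU, the enrolled patients will be followed until discharge from the hospital".
- **Section 4.4:** after 72 hours, treatment length is left to the clinical course and the investigator's judgement, with no fixed end.
- **Section 1.4, closing paragraph:** the rationale mentions a possible effect on costs, "allowing the discharge to the ward of patients with an ongoing patch".
- **Section 4.5, on the safety period:** "This period starts with the permanent discontinuation of the study drug (TTS-fentanyl) and ends 24 hours later". New adverse events in that period go into the CRF, and the patient may not leave hospital until it is over.
- **Section 5.4:** medications are recorded, with start and end dates, up to 24 hours after study drug is stopped.
- **Section 8.2:** adverse events with onset up to 24 hours after treatment ends are recorded. However, information on ongoing events that arrives after the "EOS visit will not be collected in the CRF".

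**The concern.** The plan has no single point at which data collection ends. One set of sections closes at ICU discharge. Another runs to hospital discharge, or to 24 hours after the last patch comes off. Where they disagree, the earlier date governs at least one kind of data: follow-up of adverse events that have not resolved.

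That matters here for two reasons. Section 8.1.2 says the therapeutic dose for this new use is not settled, so how events end is part of what a phase II pilot should report. The risk-benefit argument in sections 1.3 and 9 also leans on continuous ICU monitoring, and outcome collection stops exactly when the patient leaves that setting, possibly with study drug still being absorbed.

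Separately, length of hospital stay is a named secondary endpoint (section 2.4). The only visit at which it is listed comes before it can be known for any survivor transferred to a ward.

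**Working it through.** The plan gives no figure to reproduce on this point. The check sets the sections against one another on a common time line.

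**Times for one Group 2 patient**

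- T_ICU: ICU discharge, which is EOS (section 4.6, Table 1).
- T_off: permanent removal of the patch (section 4.5). It is open-ended after 72 h (section 4.4).
- T_off + 24 h: end of the safety period (section 4.5).
- T_hosp: hospital discharge, which may not precede T_off + 24 h (section 4.5).

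**Step 1: how much of the safety period falls after EOS**

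Hours after EOS = min(24, max(0, T_off + 24 − T_ICU)).

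| Patch removed | Calculation | Hours of the safety period after EOS |
|---|---|---|
| 24 h or more before ICU discharge | max(0, −24 + 24) = 0 | 0 |
| 12 h before ICU discharge (illustrative) | −12 + 24 = 12 | 12 |
| At or after ICU discharge | min(24, 24 or more) | 24 |

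The order of rows in Table 1, with safety follow-up before EOS, fits only the first line. Nothing in sections 4.4 to 4.6 guarantees that line.

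**Step 2: what is collected for each kind of adverse event**

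| Event | Is the event recorded? | Is an outcome that occurs after EOS collected? |
|---|---|---|
| Starts and resolves before EOS | Yes (8.2) | Not applicable |
| Starts before EOS, still ongoing at EOS | Yes (8.2) | No (8.2) |
| Starts on the ward, within 24 h of stopping study drug or while still on it | Yes (4.5, 8.2) | No; any follow-up necessarily arrives after EOS (8.2) |

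The adverse event form in section 8.2 has fields for outcome and date of resolution. The last rule of the same section excludes the information needed to fill them in the second and third rows. Section 4.5 speaks only of new events, and section 4.3.2 does not say that outcomes of ongoing events are gathered on the ward. No other section restores them.

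**Step 3: hospital stay and opioid duration**

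Hospital stay is fixed at T_hosp. For a survivor moved to a ward, T_hosp is later than T_ICU, so the item cannot be completed at EOS. Section 4.3.2 implies it will be obtained later, but Table 1 has no row for that and no visit is defined for it. Section 4.7 ties the end of the trial to the last subject's last visit, so that milestone can be reached while the patient is still in hospital.

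Overall opioid duration cannot be completed at T_ICU if T_off is later. Section 5.4 should still yield the patch end date, because its window is anchored to stopping study drug and not to EOS. Section 4.5 identifies study drug as TTS-fentanyl, so that window has no clear end in Group 1.

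**The case against.** The best case for the plan is that most of the data survive.

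- **Hospital stay.** A reader might infer that it is cut off at ICU discharge and that the whole ward stay is missing. Section 4.3.2 says otherwise: patients are followed until they leave hospital. What remains is an item listed at the wrong visit, with no defined collection point.
- **Patch time on the ward.** A reader might infer that it is lost. Section 5.4 records end dates until 24 h after study drug stops, so the patch end date should be in the CRF.
- **Bias between arms.** Since only Group 2 can wear a patch, a reader might infer that its opioid duration is selectively shortened. The endpoint in section 2.4 is duration of intravenous remifentanil, and section 2.3 speaks of continuous infusion. Patch time is not infusion time. Overall opioid duration appears only as an EOS data item, and no planned analysis names it.
- **New adverse events.** None is lost through the EOS definition, because the onset window in section 8.2 does not depend on EOS.
- **Ward use of the patch.** The documents present it as a possibility, not a plan. Section 9 calls it theoretical, and no frequency is given.
- **The section 8.2 rule.** It is worded alike for both arms, and the safety endpoints in section 2.5 are occurrences of events or needs for treatment, not resolutions.

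All of this stands, and it limits the point. It does not answer two things: follow-up of unresolved events is excluded by an explicit rule in patients who may still be receiving study drug, and sections 4.3.2 and 4.6 disagree about when the last data are taken.

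**Conclusion.** The point holds in a limited form. Outcomes of adverse events that are ongoing at ICU discharge, or that start on the ward within the safety period, are not collected, although the events themselves are. The recording point for hospital stay, a named secondary endpoint, contradicts the stated follow-up. The item on overall opioid duration may also be incomplete when it is due.

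The size per patient is clear: up to the full 24 h safety period lies after EOS. The number of patients is not. It ranges from none to all 12 planned for Group 2 for the safety-period overlap. The rule on unresolved events could touch any of the 24 patients. The documents give no rate of ward patch use or of unresolved events that would narrow this.

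The conclusion assumes that section 8.2 is applied as written and that some patients leave the ICU with a patch on, with one removed less than 24 h earlier, or with an unresolved event. The primary endpoint, which closes at 72 h, is untouched. The documents do not support a claim that hospital stay or patch end dates are lost, or that a listed opioid endpoint is biased. This is a cheap improvement.

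**What to change.** Reconcile sections 4.3.2, 4.5, 4.6 and 8.2 and Table 1 on one closing date for data collection:

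1. Keep the ICU-discharge assessment (blood gases, respiratory and haemodynamic parameters, GCS, RASS, ICU stay) as a scheduled visit, but do not call it the last one.
2. Define EOS as the later of hospital discharge and the end of the 24 h safety period, or death. Leave the rules on withdrawal of consent in section 7 unchanged.
3. At that point, in both arms, record hospital stay, opioid end dates (infusion and patch separately) and the outcome of every adverse event still ongoing. Add the matching row to Table 1.
4. Let the section 8.2 cut-off for follow-up of ongoing events refer to the new EOS. The milestone in section 4.7 then moves with it.

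The change concerns data collection only and alters no treatment rule. Patients are already to be followed to hospital discharge and, under section 4.5, may not be discharged before the safety period ends, so follow-up is not lengthened beyond what the plan promises. The cost is amendment wording, one CRF page filled from the hospital chart, and a slightly later data lock.

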4.7 Last Visit Last Patient (LVLP)

This visit or time point occurs when the last subject randomized into the study completes his/her last visit

The overall study design is depicted in Figures 1, 2, 3, 4, and table 1.

5. Previous and Concomitant therapy

5.1 Definitions

For this study, a previous therapy is defined as any treatment for which the end date is prior to the signature of the informed consent form. A study-concomitant therapy is defined as any treatment that is ongoing or initiated after the signature of the informed consent form or initiated up to 24 hours post-study drug discontinuation. A therapy that is study treatment-concomitant is any treatment that is either ongoing at the start of study treatment or is initiated during the treatment period until the time of permanent study drug discontinuation.

5.2 Allowed concomitant therapy

The usual standard of care for each patient is allowed except for those therapies listed in the “forbidden concomitant therapy” section and must be documented in the medical chart.

5.3 Forbidden concomitant therapy

The following medications/therapies are forbidden due to their potential to interfere with the evaluation of efficacy or safety, or due to the potential for a drug to drug interaction with study drug (TTS-fentanyl):

- Monoamine Oxidase Inhibitors (MAOI): TTS-fentanyl is not recommended for use in patients who require the concomitant administration of an MAOI. Severe and unpredictable interactions with MAOIs, involving the potentiation of opiate effects or the potentiation of serotonergic effects, have been reported. Therefore, TTS-fentanyl should not be used within 14 days after discontinuation of treatment with MAOIs;
- Serotonergic medicinal products: Co-administration of fentanyl with serotonergic medicinal products, such as a Selective Serotonin Re-uptake Inhibitor (SSRI) or a Serotonin Norepinephrine Re-uptake Inhibitor (SNRI) or a Monoamine Oxidase Inhibitor (MAOI), may increase the risk of serotonin syndrome, a potentially life-threatening condition;
- Concomitant use of mixed opioid agonists/antagonists: The concomitant use of buprenorphine, nalbuphine, or pentazocine is not recommended. They have high affinity to opioid receptors with relatively low intrinsic activity and therefore partially antagonize the analgesic effect of fentanyl and may induce withdrawal symptoms in opioid-dependent patients;
- The concomitant use of CYP3A4 inhibitors and inducers and TTS-fentanyl is not recommended because it can interfere with the drug concentrations and with the evaluation of efficacy or safety. The following substances may increase fentanyl concentrations and should be avoided: amiodarone, cimetidine, clarithromycin, diltiazem, erythromycin, fluconazole, itraconazole, ketoconazole, nefazodone, ritonavir, verapamil,

and voriconazole. The following substances may decrease fentanyl concentrations and should be avoided: carbamazepine, phenobarbital, phenytoin, and rifampicin;

- Techniques of haemofiltration and haemodiafiltration can interfere with fentanyl serum concentrations causing a potential bias in the study;
- Techniques of extracorporeal circulation can interfere with fentanyl serum concentrations causing a potential bias in the study;
- Noradrenaline infusion rates more or equal than 0.1 mcg/kg/min or Inotropes should be avoided as they can have an impact on fentanyl transdermal absorption altering microcirculation resulting in unpredictable fentanyl serum concentrations causing a potential bias in the study.

5.4 Reporting of previous/concomitant therapy in the CRF

All previous and study-concomitant therapies taken/administered less than or equal to 24 hours prior to randomization into the study will be recorded in the CRF. All medications administered randomization and up to 24 hours post-study drug discontinuation will also be recorded in the CRF. The generic name, start/end dates and times of administration, route, dose regimen, and indication will be recorded.

- Age > 18 yo
- Pregnancy test (-) if female in fertile age
 - Obtain Informed Consent
- Remifentanil infusion lasting > or = 5 days
 - On Pressure Support Ventilation

[figure not shown]

Fig 1. Screening Period

[figure not shown]
GROUP 1

Remifentanil iv alone

At each visit we will record:

- An Arterial Blood Gases (ABG) sample will be collected
- Glasgow Coma Scale, RASS, the dosage of remifentanil;
- Respiratory parameters: Ventilation mode, Pressure Support, Respiratory Rate, Tidal Volume, peep, FiO_2 , EtCO_2 , SpO_2 ; if spontaneously breathing: FiO_2 , RR, SpO_2
- Haemodynamic parameters

EAdi, flow and Paw waveforms will be recorded 1, 6, 12, 24 hours from the time of randomization for day 1 and every 24 hours for the following days.

Day 1

[figure not shown]
Visits every 4 hours

If $\text{PaCO}_2 > 45 \text{ mmHg}$ $\downarrow 0.025 \text{ mcg/kg/min}$
 If $\text{PaCO}_2 40-45 \text{ mmHg}$ $\downarrow 0.0125 \text{ mcg/kg/min}$
 If $\text{PaCO}_2 35-40 \text{ mmHg}$ $\approx \text{no changes}$
 If $\text{PaCO}_2 30-35 \text{ mmHg}$ $\uparrow 0.0125 \text{ mcg/kg/min}$
 If $\text{PaCO}_2 < 30 \text{ mmHg}$ $\uparrow 0.025 \text{ mcg/kg/min}$

Day 2 and 3

Visits every 6 hours

If $\text{PaCO}_2 > 45 \text{ mmHg}$ $\downarrow 0.025 \text{ mcg/kg/min}$
 If $\text{PaCO}_2 30-45 \text{ mmHg}$ $\downarrow 0.0125 \text{ mcg/kg/min}$
 If $\text{PaCO}_2 < 30 \text{ mmHg}$ $\uparrow 0.0125 \text{ mcg/kg/min}$

GROUP 2

Starts TTS fentanyl 50 mcg/hr and maintain remifentanil iv

[figure not shown]
EVERY 24 HOURS

- If $\text{PaCO}_2 > 45 \text{ mmHg}$ remove TTS-fentanyl 25 mcg/hr
- If $\text{PaCO}_2 35-45 \text{ mmHg}$ don't add or remove tts fentanyl
- If $\text{PaCO}_2 30-35 \text{ mmHg}$ add TTS-fentanyl 50 mcg/hr
- If $\text{PaCO}_2 < 30 \text{ mmHg}$ add TTS-fentanyl 75 mcg/hr

At each visit we will record:

- An Arterial Blood Gases (ABG) sample will be collected
- Glasgow Coma Scale, RASS, the dosage of remifentanil and TTS-fentanyl;
- Respiratory parameters: Ventilation mode, Pressure Support, Respiratory Rate, Tidal Volume, peep, FiO_2 , EtCO_2 , SpO_2 ; if spontaneously breathing: FiO_2 , RR, SpO_2
- Haemodynamic parameters

4 Hours

Day 1
Visits every 4 hours

- If $\text{PaCO}_2 > 45 \text{ mmHg}$ $\downarrow 0.025 \text{ mcg/kg/min}$
- If $\text{PaCO}_2 40-45 \text{ mmHg}$ $\downarrow 0.0125 \text{ mcg/kg/min}$
- If $\text{PaCO}_2 35-40 \text{ mmHg}$ \approx no changes
- If $\text{PaCO}_2 30-35 \text{ mmHg}$ $\uparrow 0.0125 \text{ mcg/kg/min}$
- If $\text{PaCO}_2 < 30 \text{ mmHg}$ $\uparrow 0.025 \text{ mcg/kg/min}$

Day 2 and 3
Visits every 6 hours

- If $\text{PaCO}_2 > 45 \text{ mmHg}$ $\downarrow 0.025 \text{ mcg/kg/min}$
- If $\text{PaCO}_2 30-45 \text{ mmHg}$ $\downarrow 0.0125 \text{ mcg/kg/min}$
- If $\text{PaCO}_2 < 30 \text{ mmHg}$ $\uparrow 0.0125 \text{ mcg/kg/min}$

EAdi, flow and Paw waveforms will be recorded 1, 6, 12, 24 hours from the time of randomization for day 1 and every 24 hours for the following days.

Figure 3. Treatment Period Group 2

[figure not shown]

Figure 4. Study Design

Screening Period	Verify inclusion/exclusion Criteria, Obtain Pregnancy test and Informed consent
Patient Enrolled	Baseline: ABG sample, respiratory and hemodynamic parameters, GCS, RASS, dosage of remifentanil at inclusion, 1-hour recording of EAdi, flow, and Paw
Treatment period	Randomization (group 1 remifentanil alone, group 2 remifentanil + TTS-fentanyl)
1 hour*	Recording of EAdi, flow, and Paw
4 hours* (Visit 1)	ABG sample, respiratory and hemodynamic parameters, GCS, RASS, dosage of remifentanil and TTS-fentanyl
6 hours*	Recording of EAdi, flow, and Paw
8 hours* (visit 2)	ABG sample, respiratory and hemodynamic parameters, GCS, RASS, dosage of remifentanil and TTS-fentanyl
12 hours* (visit 3)	ABG sample, respiratory and hemodynamic parameters, GCS, RASS, dosage of remifentanil and TTS-fentanyl, Recording of EAdi, flow, and Paw

16 hours* (visit 4)	ABG sample, respiratory and hemodynamic parameters, GCS, RASS, dosage of remifentanil and TTS-fentanyl
20 hours* (visit 5)	ABG sample, respiratory and hemodynamic parameters, GCS, RASS, dosage of remifentanil and TTS-fentanyl
24 hours* (visit 6)	ABG sample, respiratory and hemodynamic parameters, GCS, RASS, dosage of remifentanil and TTS-fentanyl, Recording of EAdi, flow, and Paw
30 hours* (visit 7)	ABG sample, respiratory and hemodynamic parameters, GCS, RASS, dosage of remifentanil and TTS-fentanyl
36 hours* (visit 8)	ABG sample, respiratory and hemodynamic parameters, GCS, RASS, dosage of remifentanil and TTS-fentanyl
42 hours* (visit 9)	ABG sample, respiratory and hemodynamic parameters, GCS, RASS, dosage of remifentanil and TTS-fentanyl
48 hours* (visit 10)	ABG sample, respiratory and hemodynamic parameters, GCS, RASS, dosage of remifentanil and TTS-fentanyl, Recording of EAdi, flow, and Paw
54 hours* (visit 11)	ABG sample, respiratory and hemodynamic parameters, GCS, RASS, dosage of remifentanil and TTS-fentanyl
60 hours* (visit 12)	ABG sample, respiratory and hemodynamic parameters, GCS, RASS, dosage of remifentanil and TTS-fentanyl
66 hours* (visit 13)	ABG sample, respiratory and hemodynamic parameters, GCS, RASS, dosage of remifentanil and TTS-fentanyl
72 hours* (visit 14)	ABG sample, respiratory and hemodynamic parameters, GCS, RASS, dosage of remifentanil and TTS-fentanyl, Recording of EAdi, flow, and Paw
End of observation period for the primary endpoint	72 hours after randomization

Treatment suspended	The treatment duration will be dependent on the subject's clinical course and the investigator's judgment on the perceived need to continue the study drug
Safety FU period	Permanent discontinuation of TTS-fentanyl: start of 24 hours of Safety Follow up Period (any adverse event will be recorded on the CRF)
End of Study Visit	This visit occurs at the discharge from the ICU or in case of death after the observation period for the primary endpoint ABG sample, respiratory and hemodynamic parameters, GCS, RASS, Data on the global duration of opioid therapy/length of stay (LOS) in hospital and ICU

*Hours from randomization

Table 1. Study visits and assessments

6. Statistical analysis

Distribution normality will be assessed with the Kolmogorov-Smirnov test. Continuous variables will be reported expressed as medians (interquartile ranges). Qualitative variables will be reported as frequencies.

Analysis of the primary efficacy criterion (AUC of the work of breathing) and other quantitative variables will be assessed with the Wilcoxon-Mann-Whitney sum of rank test. Categorical outcomes will be compared with the chi-square test, or Fisher's exact test, as appropriate: Cochran-Mantel-Haenszel statistics will be reported for all these results. Two-way analysis of variance (ANOVA) for repeated measures with Bonferroni correction will be used to determine the differences in work of breathing per breath, inspiratory effort, delta EAdi, plateau pressure, P 0.1 respiratory rate, tidal volume, arterial blood pressure, heart rate in the two groups. Comparisons between groups regarding these variables at each study time point will be performed with the Student's t-test or Mann-Whitney test, as appropriate. Mean difference and 95% confidence interval [CI95%] are reported for most significant results.

Two-tail p values≤0.05 Will be considered significant. Statistical analysis will be performed with SPSS software package (SPSS Inc. Released 2009. PASW Statistics for Windows, Version 18.0. Chicago: SPSS Inc.).

